7.7.2 Adverse Events

All AEs recorded on the eCRF will be coded using the MedDRA dictionary (Version 23 [or a later version if updated during the study]) and classified as TEAEs as follows:

- TEAEs are events with start date and time on or after the date and time of first dose of study drug during the double-blind Treatment Period or single-blinded Safety Follow-up Period, or events with start date and time prior to the date and time of first dose of study drug during the double-blind Treatment Period whose severity worsens on or after the date and time of first dose of study drug during the double-blind Treatment Period or single-blind Safety Follow-up Period.

All AE data will be listed by treatment group with TEAE status flagged in the listing. In addition, listings of treatment-emergent SAEs, TEAEs leading to discontinuation of study drug during the double-blind Treatment Period and TEAEs resulting in death will be produced.

Summary tables of TEAEs by treatment group and overall will be produced for the double-blind Treatment Period and the single-blind Safety Follow-up Period for the Safety population.

The relationship between an AE and study drug is assessed as definite, probable, possible, unlikely, or not related. A drug-related AE is an AE considered by the investigator as definitely, possibly, or probably related to study drug or with unknown/missing relationship to study drug.

An overview table will summarize the number and percentage of patients with at least 1 of the following TEAEs, where patients with more than 1 TEAE in a particular category are counted only once in that category:

- Any TEAE
- Drug-related TEAE
- Severe drug-related TEAE
- Treatment-emergent SAEs
- Drug-related treatment-emergent SAEs
- TEAE leading to study drug discontinuation
- Drug-related TEAE leading to study drug discontinuation
- TEAE leading to death

The number and percentage of patients reporting each AE will be summarized by SOC and PT for the Safety population. Tables will be sorted alphabetically by SOC.

Preferred terms will be sorted by descending overall total. The following summaries will be produced:

- TEAEs by SOC and PT
- TEAEs by PT
- TEAEs reported by at least 5% of patients in any treatment group, by SOC and PT
- TEAEs related to study drug, by SOC and PT
- TEAEs related to study drug, by PT
- TEAEs by relationship (related, or unrelated) to study drug, by SOC and PT
- TEAEs by severity, by SOC and PT
- TEAEs related to study drug by severity, by SOC and PT
- TEAEs causing discontinuation from study drug, by SOC and PT
- TEAEs related to study drug causing discontinuation from study drug, by SOC and PT
- Treatment-emergent SAEs, by SOC and PT
- Treatment-emergent SAEs related to study drug, by SOC and PT
- TEAEs leading to death, by SOC and PT
- SAEs during Screening or Run-in Periods leading to death, by SOC and PT
- The five Specific TEAEs and time to onset, by PT
- The five Specific TEAEs and AE duration, by PT
- The five Specific TEAEs and DPNP drug use, by PT
- The five Specific TEAEs and age category, by PT
- The five Specific TEAEs and sex, by PT
- The five Specific TEAEs and race, by PT
- The five Specific TEAEs and country, by PT

In the above summaries, patients with more than 1 AE within a particular SOC are counted only once for that SOC. Similarly, patients with more than 1 AE within a particular PT are counted only once for that PT. For summaries by severity, patients with multiple AEs within a particular SOC or PT will be counted under the category of their most severe AE within that SOC or PT. In a similar manner, summaries prepared by drug relationship will select the event with the greatest degree of relationship when a patient reports multiple occurrences of the same event.

The 5 specific TEAEs are defined in [Section 7.6.4](#). For the summary of the 5 specific AEs by subgroup in the last 7 bullets, the denominator for percentage is the number of patients with the respective specific TEAEs in the double-blind treatment period for each treatment group.

The number and percentage of patients with drug interruption due to AE in the double-blind treatment period will be summarized by treatment group for the Safety population.

No statistical comparisons of AEs between treatment groups will be performed.

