5.1.2 Run-in Period

After meeting Screening eligibility criteria, patients will enter a 2-week single-blind Run-in Period. On Day 1 of the Run-in period, patients will be administered 4 tablets of single blind study drug at the site. For the remaining duration of the Run-in Period, patients will take a single tablet of study drug in the morning. Each evening patients will rate and record the intensity of their DPNP over the previous 24 hours based on Question 5 of the BPI-DPN by answering the question "Please rate your pain due to your diabetes by indicating the one number that best describes your pain on the average." (0 [no pain] to 10 [pain as bad as you can imagine]) in their daily pain diary and will rate the interference of pain with sleep by completing Question 9F of the BPI-DPN. The ADPS will be calculated using all available daily pain diary data. In order to qualify for randomization, patients must have completed ≥70% of the daily pain diary entries during the week prior to randomization, meet criteria for moderate to severe pain, and demonstrate ≥80% compliance with taking the expected amount of placebo tablets during the Run-in Period. During the Run-in Period patients will not be allowed to use any rescue medication. On the morning of the Run-in Visit, patients may consume a light meal prior to the visit.

Note: Patients who fail Screening may be rescreened ONCE after discussion with the Medical Monitor.

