9.1.2 Serious Adverse Events

All SAEs will be collected starting with signing informed consent and continue until 35 days after the last dose of study drug.

An SAE is defined as any AE that results in any of the following outcomes:

- Death;
- A life-threatening AE defined as an event, in the view of the Investigator, the occurrence of which places the patient or patient at immediate risk of death. It does not include an AE that, had it occurred in a more severe form, might have caused death;
- Hospitalization or prolonging of an existing hospitalization;
- A persistent or significant incapacity or substantial disruption of the ability to conduct normal life functions; or,
- A congenital anomaly/birth defect.

Important medical events that may not result in death, be life-threatening, or require hospitalization may be considered serious when, based upon appropriate medical judgment, they may jeopardize the patient and may require medical or surgical intervention to prevent one of the outcomes listed above. Examples of such medical events include allergic bronchospasm requiring intensive treatment in an emergency room or at home, blood dyscrasias or convulsions that do not result in inpatient hospitalization, or the development of drug dependency or drug abuse.

Hospitalization is defined as any inpatient overnight stay in a hospital. This does not include an emergency room visit or admission to an outpatient facility.

A hospitalization in and of itself should not be reported as an SAE.

Hospitalizations for preplanned or elective surgery or routine clinical procedures without worsening of the underlying condition, or for administrative/social reasons (such as convenience, logistics) should not be reported as SAEs. However, if an elective procedure has to be performed sooner than planned due to a worsening of the underlying medical condition and the patient is hospitalized for the procedure, the worsening medical condition should be reported as an SAE.

Any laboratory abnormality fulfilling any of the criteria for an SAE should be reported as such.

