10.2.5 Safety Population

The Safety Population is defined as those patients who received any exposure to study drug.

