3.4 Safety Variables

Safety endpoints are as follows:

- Incidence of treatment-emergent adverse events (TEAEs), suspected adverse reaction, AEs leading to discontinuation from the study, serious adverse events (SAEs), and deaths
- Actual and change from Baseline in clinical laboratory results
- Actual and change from Baseline in vital signs results, including weight
- Clinically significant change from Baseline in physical examination (PE) findings
- Actual and change from Baseline in ECG findings

4. Pharmacokinetic (PK) Variables

PK endpoints from the optional PK substudy may include, but are not limited to:

- AUC_{0-24}
- $AUC_{0-t_{last}}$
- $AUC_{0-\infty}$
- AUC_{0-T}
- CL/F
- $CL/F/kg$
- C_{max}
- C_{ss}
- t_{max}
- $t_{1/2}$
- Vz/F
- λz

Biomarker samples will be collected for patients participating in the PK substudy.

5. Analysis Populations

Analysis of the primary and secondary efficacy endpoints will be based on the Modified Intent-to-Treat (mITT) population. Safety endpoints analyses will be based on the Safety population.

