5.5 Safety Population

The Safety population is defined as those randomized patients who take at least 1 dose of study drug during the double-blind Treatment Period. Safety patients are analyzed according to their actual treatment received on Study Day 1.

CONFIDENTIAL

Document Date: 07JUN2022

Page 17 of 55
ST-AD-008 version 05

6. Data Handling

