7.2 Patient Disposition and Data Sets Analyzed

Patient disposition will be listed and summarized by treatment group and overall, and will include the number and percentage of patients:

- Screened
- Entered single-blind placebo Run-in Period
- Discontinued single-blind placebo Run-in Period
- Randomized
- Randomized and not treated
- Treated
- Completed double-blind Treatment Period
- Discontinued double-blind Treatment Period
- Entered optional PK substudy
- Entered optional qualitative patient interview substudy
- Completed single-blind placebo Safety Follow-up Period
- Discontinued single-blind placebo Safety Follow-up Period

CONFIDENTIAL

Document Date: 07JUN2022

Page 23 of 55
ST-AD-008 version 05

- Included in each study population (ITT, mITT, PP, PK – Substudy, PK - C_{trough} and Safety)

The number and percentage of patients who complete the study and who discontinue early (including a breakdown of the primary reasons for discontinuation), will be presented for the ITT population. In addition, the number of patients who discontinue from the double-blind Treatment Period and single-blind Safety Follow-up Period will be summarized by treatment group, respectively.

A summary of patient enrollment by site will also be provided by treatment group and overall for the ITT population. A summary of patient enrollment by randomization strata of baseline pain severity (moderate or severe pain, based on ADPS) will also be provided by treatment group, respectively.

Randomization strata will be collected in the Interactive Voice/Web Response System (IXRS) and it is defined as the average of the scores recorded in the pain diary, ie, Question 5 of the BPI-DPN, during the 2-week single-blind Run-in Period. The rounded average score will be classified as below:

- Moderate: [5-7]
- Severe: [8-9]

A summary of the reasons for screen failure as well as the number of patients screened but not randomized will be produced. No other information for screen failures will be presented.

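### As worded, the SAP 7.7.2 table of fatal Screening and Run-in SAEs cannot count a patient who dies before randomization, so a zero there would not show that no such death occurred

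*SAP*

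**What the plan says.** SAP 7.7.2 fixes the population for its AE tables in the sentence that opens the list: "The number and percentage of patients reporting each AE will be summarized by SOC and PT for the Safety population". One entry in that list is "SAEs during Screening or Run-in Periods leading to death, by SOC and PT". No entry is exempted, and no other population is named for this one. The introduction to SAP section 5 gives the same default: "Safety endpoints analyses will be based on the Safety population".

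SAP 5.5 defines the set: "The Safety population is defined as those randomized patients who take at least 1 dose of study drug during the double-blind Treatment Period". Protocol 10.2.5 is wider: "The Safety Population is defined as those patients who received any exposure to study drug".

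On collection, Protocol 9.1.2 states: "All SAEs will be collected starting with signing informed consent". The schedule in Appendix A has SAEs recorded at the Screening and Run-in visits. Patients take tablets in Run-in, which Protocol 5.1.2 calls study drug: "For the remaining duration of the Run-in Period, patients will take a single tablet of study drug in the morning".

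For people who never reach randomization, SAP 7.2 plans counts of those screened and those who entered or discontinued Run-in, plus a summary of reasons for screen failure. It then adds: "No other information for screen failures will be presented".

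**The concern.** The title of the table and its population point at different people. The table sits beside a separate entry for treatment-emergent fatal events, so it was evidently meant to show deaths that the treatment-emergent tables leave out. The people most likely to belong in it are those who die before randomization, and the stated population removes them.

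What is at stake is how the table would be read. A study report reader who sees no events in a table of fatal SAEs in Screening or Run-in will conclude that nobody died in those periods, and under the present wording the table cannot support that conclusion. If such a death did occur, the table and the patient listings would disagree and someone would have to explain why. Run-in patients take single-blind tablets and undergo study procedures, so this is a safety result worth reporting correctly.

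**Working it through.** No sample size, error rate or event figure is involved and the plan states no number to reproduce. The check is one of set membership.

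**Inputs**
- Event: an SAE in Screening or Run-in that leads to death (SAP 7.7.2).
- Population: the Safety population (SAP 7.7.2, opening sentence of the list; same default in SAP section 5).
- Conditions for entry: randomized, and at least 1 double-blind dose (SAP 5.5).
- Capture: SAEs are collected from consent (Protocol 9.1.2; Appendix A, note g). The introduction to Protocol section 9 sends most pre-dose events to medical history but allows for exceptions specified elsewhere, and 9.1.2 is one.

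**Step 1. Go through the possible cases.**

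| SAE starts in Screening or Run-in, and the patient | Randomized | Double-blind dose | Counted in the table |
|---|---|---|---|
| dies in Screening | no | no | no |
| dies in Run-in | no | no | no |
| is randomized, dies before the first double-blind dose | yes | no | no |
| is randomized, dosed, and later dies of it | yes | yes | yes |

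**Step 2. Write the count.** Let d be the number of patients in the first three rows and e the number in the last. The true number of patients with the event is d + e. The table reports e and misses d, whatever d is. With e = 0, the table shows 0 when d = 0 and also shows 0 when d = 1.

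**Step 3. Check whether the protocol definition would help.** Protocol 10.2.5 asks only for exposure to study drug, and Protocol 5.1.2 uses that term for the Run-in tablets. Read literally, it could admit a patient who dies in Run-in. It would still exclude a patient who dies in Screening, before any tablet. SAP 5.5 closes the Run-in route by requiring randomization and a double-blind dose, and SAP section 8, which records changes in planned analysis, mentions only the NPSI model.

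**Step 4. Check the other displays.** Protocol 10.4.5.2 promises listings of deaths and SAEs with no population limit, and SAP 7.7.2 says that all AE data are listed. The specific SAE and death listings named in SAP 7.7.2 are confined to treatment-emergent events. The general AE listing is arranged by treatment group, which a patient who was never randomized does not have.

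**Step 5. After the fix.** With all consented patients as the population, the table reports d + e. SAP 7.2 already counts patients screened and patients entering Run-in, so both denominators exist.

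**The case against.** Several points on the other side are fair.

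**The table is defined by when the SAE occurred.** A reader might infer that the table must be empty whatever happens. The documents do not support that: the last row of the case table can be counted. The exclusion is certain only for patients who die without a double-blind dose, which includes everyone who dies before randomization.

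**The deaths would still be listed.** A reader might infer that these deaths vanish from the report. They should not, given Protocol 10.4.5.2 and the general AE listing in SAP 7.7.2. Arranging a listing by treatment group is a layout rule, not an exclusion. This limits the damage to one summary table, but it also means that the table and the listing could disagree.

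**SAP 7.2 may not apply.** Its screen-failure sentence sits in the disposition section, and that section does not say whether a patient who dies after entering Run-in is a screen failure. A general disposition sentence need not override a safety table that is listed by name. This stands as an ambiguity, and a short exemption would settle it.

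**Table shells may name another population.** SAP 7.1 lets its principles be restated elsewhere and lets shells change percentage denominators. The shells are not among the documents, so this cannot be ruled out. Nothing in SAP 7.7.2 points to a different population for this entry, and a changed denominator would not by itself bring excluded patients into the numerator.

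**Size and scope.** A reader might try to size the problem from a guessed screen-failure rate. The Amendment 4 summary says that the rate was higher than expected but gives no figure, and a head count of people outside the population is not a count of missed deaths. A reader might also infer that a table of non-fatal pre-randomization SAEs is owed. The documents promise none, so its absence breaks no commitment.

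**Conclusion.** The concern holds in a limited form. Under the SAP text, no patient who dies before randomization can be counted in the one table titled to cover fatal SAEs in those periods, so a zero in it would not show that there were no such deaths. This follows from a stated population rule and is more than missing detail. The size is d missed patients, where d is not knowable from the documents and may well be 0.

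The conclusion rests on two readings: that the opening sentence of the list in SAP 7.7.2 governs every entry below it, and that no table shell overrides it. The effect is confined to the summary of pre-randomization deaths. Efficacy, the treatment-emergent tables and the between-arm safety comparisons are unaffected. Severity: minor.

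**What to change.** 1. In SAP 7.7.2, state that this one table uses all consented patients, with a single Total column in place of treatment groups, and denominators for patients screened and patients who entered Run-in.
2. In SAP 7.2, exempt SAEs and deaths from the sentence that limits what is shown for screen failures.
3. Reconcile SAP 5.5 with Protocol 10.2.5. The simplest course is to keep the SAP definition for the between-arm tables, where every patient needs a treatment group, and record the narrowing in SAP section 8.

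The cost is a few lines of SAP text and one table shell. The SAEs are already collected from consent and the denominators are already planned, so no new data are needed.

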7.1 General Principles

All data processing, summarization and analyses will be performed using Hosted SAS Environment / Version 9.4 (or later) of the SAS® (SAS Institute, Cary, NC) statistical software package.

The following principles will be applied to all tables, figures, and listings (TFLs) unless otherwise stated:

Principle	Value
Significant tests	2-sided and use a 5% significance level for the main effect of study treatment
Treatment group labels and order presented	Placebo LX9211 100 mg/10 mg LX9211 200 mg/20 mg Total (if applicable)
Tables	Data in summary tables presented by study drug group, assessment (where applicable) and visit (where applicable)
Listings	All data collected presented by study drug group, center, patient, and visit (where applicable), date, unless otherwise specified
Descriptive summary statistics for continuous variables	Number of patients/observations with non-missing data (n), mean, standard deviation (SD), median, minimum and maximum. If n=0 then other statistics will be blank.
Descriptive summary statistics for categorical variables	Frequency counts and associated percentages [n (%)] presented to 1 decimal place.
Denominator for percentages	Number of patients in the analysis population, unless stated otherwise in table shell(s)
Include "Missing" as category	Yes, when the number missing is greater than 0 for at least 1 treatment group
Display for 0 percentages	Leave Blank
Display for treatment compliance and percentage change from Baseline	Present mean and median to 1 decimal place and SD to 2 decimal places
Display to 1 more decimal place than collected value	Mean Mean Difference Median Confidence Interval

Statistical Analysis Plan Final v3.0

Lexicon Pharmaceuticals, Inc.
Protocol ID: LX9211.1.201-DPN

Labcorp Study ID: 000000198624

Principle	Value
Display to 2 more decimal places than collected value	SD Standard Error
Display for p-values	x.xx for p-value > 0.05 x.xxx for p-value ≤ 0.05 and ≥ 0.001 <0.001 for p-value < 0.001
Limit of precision for displays	3 decimal places
Date Format	DDMMYY YYYY
Display for analysis not done	NC (not calculated), NA (not applicable), ND (not done), or NR (not reported). Refer to table shells.

For continuous efficacy variables that are derived as percentage change from Baseline outcomes, the applied analyses and their results will be used for descriptive purposes.

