7.6.4 Subgroup Analysis

The primary endpoint will be analyzed using the mITT population for the following subgroups:

- Baseline pain severity based on the actual stratum, moderate or severe
- Sex, male or female
- DPNP drug use, yes or no
- Subjects who experience the 5 specific TEAEs, yes or no

DPNP drug use subgroup is defined as those who took concomitant DPNP medications including the following: pregabalin, gabapentin, duloxetine, amitriptyline, venlafaxine, desvenlafaxine, valproic acid.

The 5 specific TEAEs refer to the AEs: dizziness, headache, nausea, somnolence, and balance disorder, which usually occur more frequently than other AEs.

The same MMRM covariates used for the primary endpoint analysis will be used for the subgroup analyses except that for the Baseline pain severity subgroup analysis, the randomization stratum of Baseline pain severity (moderate, severe) will not be included as a covariate. A forest plot of the LS Means difference and 95% CI for the

comparison of LX9211 versus placebo with the change from Baseline scores will be presented for all subgroups.

All subgroup analyses will be exploratory.

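### Tables of the five specific TEAEs by DPNP drug use, age, sex, race and country divide by patients with the event, so their percentages show case mix and do not directly show incidence within a subgroup

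*SAP*

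**What the plan says.** The list of adverse event summaries in SAP 7.7.2 ends with seven tables on five chosen events. SAP 7.6.4 defines these: "The 5 specific TEAEs refer to the AEs: dizziness, headache, nausea, somnolence, and balance disorder". Four of the seven cover DPNP drug use, age category, sex and race; the one on sex, for instance, is listed as "The five Specific TEAEs and sex, by PT". The other three are time to onset, AE duration and country.

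One sentence sets the percentage base for all seven. It opens "For the summary of the 5 specific AEs by subgroup in the last 7 bullets" and continues that "the denominator for percentage is the number of patients with the respective specific TEAEs in the double-blind treatment period for each treatment group". This departs from the general rule in SAP 7.1, under which percentages are taken of the analysis population unless a table shell says otherwise.

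Three other places bear on the point:

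- SAP 7.7.2 also plans TEAE tables by SOC and PT, and by PT, for each arm on the Safety population.
- SAP 7.4 tabulates sex, race, age (below 75, 75 or over) and DPNP drug use by arm on the mITT population.
- The protocol synopsis places all of the approximately 45 sites in the US.

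**The concern.** A table of an adverse event by sex or by background pain drug is normally read as showing whether the event is more common in one group than in another. That needs incidence: patients in the subgroup with the event, divided by patients in the subgroup. The SAP's denominator gives a different quantity: patients in the subgroup with the event, divided by all patients in the arm with the event. Within an arm these percentages add to 100% across subgroups, and a large subgroup will usually show a large percentage whatever its risk.

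The comparison most exposed to this is background drug use. Protocol 5.1 lets patients continue pregabalin, gabapentin and antidepressants, and protocol 3.1 names dizziness and somnolence among the side effects of available analgesics. No other listed summary gives the incidence of these events within subgroups. The subgroup analysis in SAP 7.6.4 splits the pain endpoint by whether a patient had one of the events, which is another question. At stake is a misreading of the safety tables, not any test or decision rule.

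**Working it through.** There is no stated figure to reproduce; the check is on a definition.

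**Inputs.** The arm size is 94 (SAP 2.3): 75 / (1 − 0.20) = 93.75, rounded up to 94, and 3 × 94 = 282, as the SAP states. The documents give no subgroup sizes or event risks. All of those below are assumptions for illustration.

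**Formulas.** For subgroup g in one arm, with e_g patients with the event, n_g patients in the subgroup and E the sum of e_g over subgroups:

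- SAP percentage = e_g / E
- Incidence = e_g / n_g

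**1. Equal risk.** If every subgroup has risk r, then e_g = r × n_g and the SAP percentage is r × n_g / (r × 94) = n_g / 94. The risk cancels.

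| Men of 94 | SAP percentage, men | SAP percentage, women |
|---|---|---|
| 47 | 50.0% | 50.0% |
| 56 | 59.6% | 40.4% |
| 66 | 70.2% | 29.8% |
| 75 | 79.8% | 20.2% |

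The same row results whether the risk is 10%, 20% or 30%.

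**2. Level of risk not shown.** With 47 men and 47 women, 3+3, 12+12 and 18+18 cases all print as 50% and 50%. Incidence is 3/47 = 6.4%, 12/47 = 25.5% and 18/47 = 38.3%.

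**3. Ranking reversed.**

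| Assumed split of 94 | Cases | SAP percentage | Incidence |
|---|---|---|---|
| 64 men, 30 women (risks 20%, 40%) | 12.8 ≈ 13 and 12 | 13/25 = 52%, 12/25 = 48% | 13/64 = 20.3%, 12/30 = 40.0% |
| 66 men, 28 women | 10 and 8 | 55.6%, 44.4% | 15.2%, 28.6% |
| 8 aged 75 or over, 86 younger | 4 and 16 | 20%, 80% | 50.0%, 18.6% |

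In each row the subgroup with the lower incidence prints the higher percentage. In the second row the women-to-men incidence ratio is 1.89.

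**4. Country.** With every site in the US there is one country, so e_g = E. The table prints 100% for any term with at least one case, in every arm and at any incidence.

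**5. Time to onset and duration.** These exist only for patients who had the event, so patients with the event are the right base there.

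**The case against.** The SAP never says what these tables are for. It lists them in one block with time to onset and duration, under one denominator sentence, which fits a description of the cases (when, how long, in whom). Protocol 10.4.5.1 asks for TEAE incidence by term and treatment group, not by patient characteristic. That stands: the aim of finding patients at higher risk is a natural reading but an inferred one. Even so, the SAP itself describes the tables as being by subgroup.

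A reader might go further and infer that the arms can no longer be compared on these events. The documents do not support that, because the SOC and PT tables give each event's incidence per arm on the Safety population.

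A reader might also infer that subgroup risk cannot be recovered at all. That too is unsupported. SAP 7.1 requires counts alongside percentages, and the baseline table in SAP 7.4 gives the size of the sex, race, age and drug-use groups, so an approximate incidence is one division away. In the first row of the reversal table, women are 30/94 = 32% of the arm but 48% of the cases, which a careful reader would notice. The division is only approximate because the baseline table uses mITT patients by randomized arm (SAP 5.2) and the AE tables use Safety patients by actual treatment (SAP 5.5). Both sets are randomized patients with at least one dose, so the gap should be small. SAP 7.7.2 also leaves age category undefined.

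The table shells are not part of the documents. Whether they print subgroup Ns cannot be checked.

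**Conclusion.** The point holds, as a fault in the percentages of five descriptive tables. As specified, the DPNP drug use, age category, sex, race and country tables print shares of cases. These follow subgroup size to a large extent, do not directly show incidence, and can order subgroups opposite to their risk. The country table carries no information in its percentages.

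The size of the distortion depends on subgroup sizes and risks that the documents do not give. The definition and the cancellation of risk in step 1 need no assumed numbers; the illustrations do, and only the arm size of 94 comes from the SAP. The reversals need unequal subgroup sizes, and one of them turns on 13 against 12 cases.

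The consequence is limited. SAP 7.7.2 plans no statistical comparison of adverse events between arms, and the primary endpoint, the futility rule and the overall AE incidence tables are untouched. The change is worth making because the printed percentage is easily misread and correcting it is cheap.

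**What to change.** Replace the single denominator sentence in SAP 7.7.2 with two rules:

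- For the summaries by DPNP drug use, age category, sex, race and country, the denominator is the number of Safety patients in the same subgroup and treatment group. That N is shown in the table.
- For time to onset and AE duration, the denominator remains the number of patients with the respective event in that arm during the double-blind period.

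Country must be named in the first rule, or it would be left without a denominator. It would help to state in the same place which age cut applies, since SAP 7.4 gives one and 7.7.2 does not.

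The cost is a short SAP edit and a change of denominator in programming. No new data are needed.
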